8.2 Derived Dates

- Start date of any study therapy is the earliest start date of BMS-955176, TDF, ATV, RTV or DTG identified from dosing records with non-missing start date. This date is used to identify treated subjects and to distinguish pre-treatment from any on-study measurements.
- Start date of continuation dosing of study therapy for BMS-955176 is the earliest start date of the continuation dose(s) of BMS-955176 with non-missing daily dose and non-missing start date. This date is used to identify treated subjects receiving the continuation dose(s) of BMS-955176 and to distinguish on-study measurements in the original dosing period from on-study measurements in the continuation dosing period.
- Start date of serum lipid-reducing agents is the earliest start date of any concomitant or post-treatment medication from the therapeutic class ‘serumlipidreducing agent’. This date is used to exclude data in longitudinal lipid analyses during treatment.
- Analysis week date is the start date of study therapy plus the upperbound of the window defining the analysis week minus 1 day (see [Section 8.1](#)). This date is used to include data through the analysis week.

8.3 Derived Parameters

When deriving a parameter that requires more than one test measurement, the parameter must be derived using measurements from the same collection date, accession number and site code for each test.

8.4 Study Therapy

Time on therapy for each individual drug component is calculated from the first and last dates of dosing, regardless the interruptions. The first date of dosing is the minimum of the dosing start dates, and the last date of dosing is the maximum of dosing stop dates.

8.5 Concomitant Medications

Start and stop date of all concomitant medications are collected on the CRF. In order to classify medication as prior, current or concomitant, partial, missing or invalid start and stop dates will be imputed where possible as follows:

- If the reported start date is missing or invalid and the informed consent date is not missing or invalid, then the imputed start date is set equal to the informed consent date. If the consent date is missing or invalid and the birth date is not missing or invalid, then the imputed start date is set equal to the birth date. If the start date, the consent date and the birth date are all invalid or missing, then the imputed start date is set equal to missing.
- If the reported start date is partially entered, then the imputed start date is set equal to the earliest possible reported start date based on the partial entered reported start date.
- If the reported end date is missing, continuing, unknown or invalid, then the imputed end date is set equal to the most recent database extraction date.
- If the reported end date of the medication is partial, then the imputed end date is set equal to the last possible reported end date based on the partial entered reported end date.

Imputed dates will not appear on the listings of non-study medication.

8.6 Counting Rules for Adverse Events

Where a subject has the same adverse event, based on preferred term, reported multiple times in a single analysis period, the subject will only be counted once at the preferred term level in adverse event frequency tables.

Where a subject has multiple adverse events within the same system organ class in a single analysis period, the subject will only be counted once at the system organ class level in adverse event frequency tables.

When a subject has the same adverse event, based on preferred term, reported multiple times in a single analysis period, the following criteria, in order of precedence, will be used to select the event to be included in the summary tables:

- Relationship to study medication: related events will take precedence over unrelated events.
- Intensity of the event: more intense events will take precedence over less intense events.
- Onset date and time: earlier onset date/time events will take precedence over late onset date/time events.

When reporting adverse events by intensity, summary tables will also be provided based on the most intense event during the analysis period - independent of relationship to study medication. For these tables, the following criteria, in order of precedence, will be used to select the event to be included in the summary tables:

- Intensity of the event
- Onset date and time

8.7 Pharmacokinetic Evaluations

8.7.1 *Decimal Places for Pharmacokinetic Data*

The number of decimal places displayed in all listings will be determined by the number of decimal places in the raw data.

Unless otherwise specified, minimum and maximum will be reported to the precision as the data collected, one more decimal place for the mean and median, and two more decimal places for the standard deviation. The adjusted geometric mean, geometric mean ratio and the lower and upper limits of confidence interval will be displayed to three decimal places.

8.7.2 *Pharmacokinetic Summaries*

In-text Tables

For in-text pharmacokinetic tables, coefficient of variation (% CV) will be reported as integers. For other statistics, values of 100 or higher will be presented as integers, values of 10 - < 100 will be displayed to one decimal place, and values of 1 - < 10 will be displayed to two decimal places. Values less than 1 will be displayed to three decimal places. Ratios will also be displayed to three decimal places.

Handling of Non-Quantifiable Concentrations

For the summaries of plasma concentration-time data, concentrations that are less than the lower limit of quantification (LLOQ) should be displayed as “< LLOQ” in the listings and be treated as missing in summary tables and plots. For the purpose of calculating intensive PK parameters, pre-dose concentrations that are less than LLOQ and concentrations prior to the first quantifiable concentration that are less than LLOQ will be set to zero, and all other concentrations less than LLOQ will be set to missing.

Sparse PK concentrations for PK/PD and PK/VK correlations will be calculated by imputing values less than LLOQ as $\frac{1}{2} * \text{LLOQ}$.

All available plasma concentration-time data and derived pharmacokinetic parameter values will be included in the PK data set and listed accordingly.

Treatment of Outliers

Individual plasma concentrations, if deemed to be anomalous, may be excluded from the analysis following a review of available documentation (e.g., bioanalytical report, clinical data). Any such exclusion will be clearly listed in the study report along with justification for exclusion.

Entire plasma concentration-time profiles for a subject may be excluded following review of available documentation (e.g., bioanalytical report, clinical data). However, results of analysis with and without the excluded profiles may be presented in the study report. Any such exclusion will be clearly listed in the study report along with justification for exclusion.

PK Exclusions

Exclusion of one or more parameters or the entire dataset may be considered due to incomplete profile, or there is no sample around the suspected C_{max}. In addition, subjects may be excluded from the analysis if they missed doses, had diarrhea, or vomited at or before a time equal to twice the median T_{max} for immediate-release products, or vomited at any time during sampling after the administration of modified-release formulations.

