4.2 Secondary Endpoints

- Proportion of subjects with plasma HIV-1 RNA < 40c/mL at Weeks 48 and 96, assessed using the snapshot algorithm
- Proportion of subjects with plasma HIV-1 RNA < 200c/mL at Weeks 24, 48 and 96, assessed using the snapshot algorithm
- Emergence of HIV drug resistance among samples selected for drug resistance testing will be assessed using the most recent version of the IAS-USA list of HIV-1 drug resistance mutations
- Changes from baseline in \log_{10} HIV-1 RNA and in CD4+ T-cell counts, and changes in the percentage of CD4+ T-cells over time will be assessed using on-treatment laboratory results, and pre-specified visit windows
- Frequency of SAEs and AEs leading to discontinuation will be tabulated directly from the case report forms (CRFs). The summary will count the number of subjects that have at least one event
- Occurrence of new AIDS defining events will be tabulated from the CRFs. The summary will count the number of subjects that have at least one event
- Steady state PK parameters of BMS-955176: C_{\max} , T_{\max} , C_{τ} , C_0 and AUC(TAU) will be assessed using the intensive PK data, collected at Week 2 from a subset of subjects

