7.10 Pharmacokinetics

The following intensive PK parameters will be summarized (using mean, SD, median, minimum, maximum, geometric mean and %CV) for BMS-955176, DTG and ATV by treatment arm:

- C_{max} : maximum observed plasma concentration
- T_{max} : time of maximum observed plasma concentration
- C_{tau} : observed plasma concentration at the end of a dosing interval
- C_0 : observed pre-dose plasma concentration
- AUC(TAU) area under the concentration-time curve in one dosing interval

The Pharmacokinetic (PK) population will be used for all listings. Evaluable PK population will be used for summary statistics and statistical analyses.

Subject plasma concentration-time profiles will be listed and summarized by treatment arm and nominal collection time for each analyte. Plots of individual plasma concentration profiles over time will be provided. Overlay of individual plasma concentration profiles over time will be provided by treatment arm. Plots of mean (+SD) plasma concentration profiles versus time will be presented for each analyte, and all treatments will be superimposed on the same plot for the analyte.

All individual PK parameters will be listed for each analyte including any exclusions and reasons for exclusion from summaries. Summary statistics will be tabulated for each PK parameter by treatment arm. Geometric means and coefficients of variation will be presented for C_{max} , AUC(TAU), C_{tau} , and C_0 . Medians and ranges will be presented for T_{max} .

The effect of BMS-955176 on the exposure of DTG (in the presence of ATV/RTV 300/100mg) will be estimated by the geometric mean ratio, with 90% confidence interval, of the exposure data in Arm 1 over the reference ATV/r arm (Arm 2). These estimates will be generated using general linear models fitted to log-transformed data. The effect of BMS-955176 on the exposure of DTG (in the presence of ATV 400mg) will be estimated by the geometric mean ratio, with 90% confidence intervals, of the exposure data in Arm 3 and Arm 4, separately, over historical data. These estimates will be generated using general linear models fitted to log-transformed data.

The population PK, exposure-response and viral kinetic analyses will be described in a separate analysis plan. Intensive and sparse pharmacokinetic data will be used in population PK, PK/PD and PK/VK.

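### In version 2.0, a Week 2 trough below LLOQ becomes zero as C0 but missing as Ctau, although both are summarised by geometric mean

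*SAP*

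**What the plan says.** Section 7.10 of version 2.0 defines C0 as the "observed pre-dose plasma concentration" and Ctau as the "observed plasma concentration at the end of a dosing interval". Of the summary statistics it says "Geometric means and coefficients of variation will be presented for" Cmax, AUC(TAU), Ctau and C0. The effect of BMS-955176 on DTG exposure is estimated by geometric mean ratios from linear models on log-transformed data. The data presentation plan applies these ratios to DTG Cmax, Ctau and AUC(TAU).

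Section 4.2 lists "Steady state PK parameters of BMS-955176", including Ctau and C0, among the secondary endpoints, taken from intensive sampling at Week 2. Section 2.1 gives once-daily dosing and about 12 substudy participants per arm.

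Section 8.7.2 has three treatments of values below LLOQ:

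- Concentration-time summaries and plots: missing.
- Intensive PK parameters: pre-dose values, and values before the first quantifiable one, found to be "less than LLOQ will be set to zero, and all other concentrations less than LLOQ will be set to missing".
- Sparse samples: "Sparse PK concentrations for PK/PD and PK/VK correlations will be calculated by imputing values less than LLOQ as" half the LLOQ.

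No sentence says how a zero C0 is to enter a geometric mean.

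**The concern.** Setting a pre-dose value to zero suits a first dose, when no drug is on board. At Week 2 with once-daily dosing, C0 and Ctau are both steady-state troughs, one dosing interval apart. Under the written rule the same low trough counts as zero at the start of the interval and is deleted at the end of it. Neither treatment fits a geometric mean: zero has no logarithm, and deletion removes values because they are low.

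C0 and Ctau of BMS-955176 are secondary endpoints, and DTG Ctau enters the interaction ratio. Section 2.1 also has the Week 24 pharmacokinetics examined before Stage 2 starts. An overstated trough errs in the reassuring direction.

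**Working it through.** The plan states no figure to reproduce. It gives no LLOQ, no below-LLOQ rate and no between-subject variability, so those are assumptions below. From the plan come n = 12 per arm, the zero and missing rules, and the geometric mean.

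**C0.** The geometric mean is exp(mean of log x). With one zero among 12 values, log 0 is minus infinity and the geometric mean is exactly 0; software that rejects log 0 either returns nothing or drops the value. The chance that an arm meets this, for a below-LLOQ rate p, is 1 − (1 − p)^12:

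| Assumed p | Chance of at least one in 12 |
|---|---|
| 1% | 11% |
| 2% | 22% |
| 5% | 46% |
| 10% | 72% |

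**Ctau.** Take troughs as lognormal with σ = √ln(1 + CV²), and let a fraction q lie below LLOQ and be dropped. The geometric mean of what remains, relative to the true one, is exp[σ·φ(z_q)/(1 − q)], where z_q is the standard normal q-quantile and φ the standard normal density.

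- σ is 0.385 at CV 40%, 0.555 at 60% and 0.833 at 100%.
- φ(z_q)/(1 − q) is 0.1086 at q = 5% and 0.195 at q = 10%.
- Example: CV 40%, q = 5% gives exp(0.385 × 0.1086) = 1.043. CV 100%, q = 10% gives exp(0.833 × 0.195) = 1.176.

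| Assumed CV | q = 5% | q = 10% |
|---|---|---|
| 40% | 1.043 | 1.078 |
| 60% | 1.062 | 1.114 |
| 100% | 1.095 | 1.176 |

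The upward bias is therefore about 4-18% over this range. Simulation with 12 subjects agrees: at CV 60% the median geometric mean after dropping is 1.059 times the true value at q = 5%, and 1.111 at q = 10%.

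**DTG Ctau ratio.** The ratio is distorted by the inflation in one arm divided by that in the reference. At CV 60%, 10% dropped in the numerator and none in the reference gives 1.114 / 1 = 1.114. Equal losses with equal spread cancel.

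**Half the LLOQ instead.** In the same simulations (n = 12, CV 60-100%, 5-20% below LLOQ), imputing half the LLOQ gave a median geometric mean of 0.93-0.99 times the true value, against 1.06-1.33 for dropping.

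**The case against.** The strongest objection is scope. The appendix of 9 November 2017 supersedes version 2.0 for the final analysis. Its section 2 says PK endpoint analyses will not be performed, and its section 3.2.3 keeps only the plasma concentration listings (Listings 34-36), where values below LLOQ are simply shown as such. This stands. A reader might infer that the final report's PK results are distorted; the documents do not support that. What remains is the set of Week 24 PK outputs planned under version 2.0, and the documents do not show whether those were produced.

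Other points on that side:

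- **Visibility.** The version 2.0 tables show N, median, minimum and maximum, so a dropped Ctau lowers N and a zero C0 appears as the minimum. That helps a careful reader but does not correct the geometric mean or the ratio.
- **Exclusions.** Section 8.7.2 lets subjects who missed doses be excluded, which may remove some very low troughs. The provision is discretionary.
- **Different rules for different purposes.** Half the LLOQ for sparse samples does not contradict another rule for intensive parameters. This is right. The fault is that zero and missing do not suit a geometric mean of steady-state troughs.
- **Not every low Ctau is dropped.** If a whole profile is below LLOQ, Ctau can be read as falling under the zero clause. The missing rule then applies only after a quantifiable value.

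Two further inferences should be resisted. A reader might measure the bias against half-LLOQ imputation: one of 12 dropped, with the others at 10 times LLOQ, gives (10/0.5)^(1/12) = 1.28. That is the distance between two conventions, not the error against the true value. With lognormal troughs at CV 100%, the chance of any such value among 12 is also only about 3%. A reader might also suppose that the unboosted ATV arms are most exposed; the SAP gives no trough or LLOQ values from which to say so.

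**Conclusion.** The defect is real but minor. The rule as written gives a zero or undefined C0 geometric mean, and an upward-biased Ctau geometric mean, whenever a Week 2 trough is below LLOQ (for Ctau, after a quantifiable value). The size of about 4-18% for Ctau rests on assumed below-LLOQ rates of 5-10%, CVs of 40-100% and lognormal troughs; it is nil if no trough is below LLOQ. C0 is affected in the summary tables only, since the planned DTG ratios do not include it. The primary endpoint and the futility tests do not use these parameters. The scope is the Week 24 PK outputs under version 2.0.

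**What to change.** Add one sentence to section 8.7.2: for the C0 and Ctau summaries and the DTG Ctau ratio, handle troughs below LLOQ the same way at both ends of the interval, for example by setting them to half the LLOQ as is already done for sparse samples, and report the number imputed by arm and analyte. Keep the zero/missing rule for the concentration-time points used in AUC(TAU).

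The cost is one sentence and one count per table. The downside is a simple imputation in place of omission, which the count makes visible. Nothing changes if no trough is below LLOQ. The concentration listings kept by the 2017 appendix need no change; the edit matters only if the Week 24 PK parameter outputs were or will be reported.

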9 REFERENCES

An interim analysis will be conducted after the last randomized subject in Stage 1 is on treatment for 24 weeks. The analyses related to the first 24 weeks of treatment for Stage 1 will be performed.

An interim analysis might be conducted after the last randomized subject in Stage 1 is on treatment for 48 weeks in case the continuation dose couldn't be selected based on the Week 24 results.

An interim analysis will be conducted after the last randomized subject in Stage 2 is on treatment for 24 weeks. The expectation is that the last subject in Stage 1 will have completed the Week 96 visit by that time. The analyses related to the first 24 weeks of treatment for Stage 2 will be performed as well as all analyses related to Stage 1 (except the futility analysis).

An interim analysis will be conducted after the last randomized subject in Stage 2 completes the Week 48 visit. The analyses related to the first 48 weeks of treatment for Stage 2 will be performed.

The final analysis will be conducted after the last randomized subject in Stage 2 completes the Week 96 visit. All analyses described in this plan will be performed for both Stages (except the futility analysis). This includes the integrated summaries described in [Section 7.8](#).

APPENDIX 1 SNAPSHOT ALGORITHM

The snapshot algorithm is described in detail in Appendix A of the CDER (2013) draft guidance on developing antiretroviral drugs¹. If the draft guidance is superseded, and development timelines permit any needed changes, then the instructions from the new guidance should be followed.

In some sections of the draft guidance, the responder cutoff is listed as HIV-1 RNA “< 50copies/mL”. This is a carryover from earlier days when the assay limit of detection was 50. Currently approved assays have lower limits. Hence, in implementing the snapshot algorithm, the assay limit of detection will replace the HIV-1 RNA limit of “< 50copies/mL”.

The analysis visit windows that appear in Table A of the draft guidance (line 1205) appear to use Day 0 as the start date. Windows that use Day 1 as the start date are in the following table.

Table 9-1: Snapshot Algorithm Analysis Visit Windows

VISIT	Window in Weeks (Weeks indicate end of study week)	Days (Inclusive of start & end points)
Week 24	18 through 30	127 through 210
Week 48	42 through 54	295 through 378
Week 96	90 through 102	631 through 714

Each snapshot analysis includes a summary of virologic outcomes at an analysis visit (e.g., Week 24) that has the same format as Table B (line 1209) of the draft guidance.

Each snapshot analysis may also include a summary of expanded virologic outcomes at an analysis visit. This summary has a similar format to Table B, but also displays the 95% CI for the response category “HIV-1 RNA < 40c/mL”, and breaks down the failure category “HIV RNA ≥ 40c/mL” into 4 subcategories. Virologic outcomes are summarized according to the following categories:

- HIV-1 RNA < 40c/mL
- HIV-1 RNA ≥ 40c/mL
 - HIV-1 RNA ≥ 40c/mL in Week 24 window
 - Discontinued study/study drug due to lack of efficacy. This includes subjects who discontinued study therapy due to lack of efficacy at any time from Day 1 through the Week 24 window if this resulted in no on-treatment HIV-1 RNA in the window.
 - Discontinued study/study drug due for other reasons. This includes subjects with last on-treatment HIV-1 RNA ≥ 40c/mL who discontinued study therapy due to any reason except AE, death and lack of efficacy at any time from Day 1 through the Week 24 window if this resulted in no on-treatment HIV-1 RNA in the window.

- No virologic data in Week 24 window
 - Discontinued study/study drug due to AE or death. This includes subjects who discontinued study therapy due to AE or death at any time from Day 1 through the Week 24 window if this resulted in no on-treatment HIV-1 RNA in the window.
 - Discontinued study/study drug for other reasons. This includes subjects with last on-treatment HIV-1 RNA $< 40\text{c/mL}$ who discontinued study therapy for other reasons (withdrew consent, lost to follow-up, moved, etc.) at any time from Day 1 through the Week 24 window if this resulted in no on-treatment HIV-1 RNA in the window.
 - On study but missing data in window

Each snapshot analysis may also include a by-subject listing that facilitates finding the subjects in each outcome category. The listing includes: subject ID; age/gender/race; as-randomized treatment group; assessment day; HIV-1 RNA on day of assessment; virologic outcome (HIV-1 RNA $< 40\text{c/mL}$, HIV-1 RNA $\geq 40\text{c/mL}$, or no virologic data in window); virologic outcome specification (see subcategories in the expanded virologic outcome summary); day of discontinuation of study therapy; and the reason for discontinuation of study therapy. The listing is sorted and paged by treatment group. Within treatment group, the subjects are sorted by virologic outcome and then by the virologic outcome specification.

An analysis data set contains at least the information specified starting on line 1346 (“Datasets for Snapshot Approach”). This analysis data set may contain additional variables, and have multiple uses besides the snapshot analysis.

APPENDIX 2 GENOTYPIC AND PHENOTYPIC RESISTANCE

Genotypic Resistance

Genotypic resistance will be assessed by searching for all:

- RT substitutions
- PI substitutions
- Integrase (IN) substitutions

that are listed in the most current version of the International AIDS Society-USA (IAS-USA) list.

The following table was prepared relative to the IAS-USA list from June/July of 2014⁵. The table describes the categories and subcategories, by which the substitutions will be categorized. In the table below, slashes (“/”) between amino acid codes do indicate mixtures. The slashes indicate that any of the amino acids in the list qualify as substitutions.

Table 9-2: Genotypic Substitutions

Category	Description of Relevant Substitutions
Protease Gene Any PI substitution	At least one of the PI substitutions listed in the IAS-USA. L10C/F/I/R/V, V11I, G16E, K20I/M/R/T/V, L24I, D30N, V32I, L33F/I/V, E34Q, M36I/L/V, K43T, M46I/L, I47A/V, G48V, I50L/V, F53L/Y, I54A/L/M/S/T/V, Q58E, D60E, I62V, L63P, I64L/M/V, H69K/R, A71I/L/T/V, G73A/C/S/T, T74P, L76V, V77I, V82A/F/I/L/S/T, N83D, I84V, I85V, N88D/S, L89I/M/V, L90M, I93L/M
Major PI Substitutions	Any of the major PI substitutions listed in the IAS-USA D30N, V32I, M46I/L, I47A/V, G48V, I50L/V, I54L/M, Q58E, T74P, L76V, V82A/F/L/S/T, N83D, I84V, N88S, L90M Major PI substitutions are sub-tabulated by codon.
Minor PI Substitutions	Any of the minor PI substitutions listed in the IAS-USA L10C/F/I/R/V, V11I, G16E,

Table 9-2: Genotypic Substitutions

Category	Description of Relevant Substitutions
	
K20I/M/R/T/V, L24I, L33F/I/V, E34Q, M36I/L/V, K43T, F53L/Y, I54A/S/V/T, D60E, I62V, L63P, I64L/M/V, H69K/R, A71I/L/T/V, G73A/C/S/T, V77I, V82I, I85V, N88D, L89I/M/V, I93L/M
 
Minor PI substitutions are sub-tabulated by codon.

Reverse Transcriptase Gene Any RT substitution	At least one of the nRTI or NNRTI substitutions listed in the IAS-USA. RT substitutions are sub-tabulated into nRTI and NNRTI substitutions.
nRTI	At least one of the nRTI substitutions listed in the IAS-USA nRTI substitutions are further sub-tabulated into: 69 Insertion Complex, 151 Complex, TAMS and Other.
69 insertion complex	Substitution at codon 69 with a double amino acid insertion and at least one of the following: M41L, A62V, K70R, L210W, T215Y/F, K219Q/E
151 complex	Q151M and at least one of the following: A62V, V75I, F77L, F116Y
Thymidine Analogue-Associated Mutations (TAMS)	At least one of the following: M41L, D67N, K70R, L210W, T215Y/F, K219Q/E
Other	At least one of the other nRTI substitutions not covered above: K65R/E/N, K70E, L74V, Y115F, M184V/I
NNRTI	At least one of the substitutions listed in the IAS-USA for any of the NNRTIs: V90I, A98G, L100I, K101E/H/P, K103N/S, V106A/I/M, V108I, E138A/G/K/Q/R, V179D/F/L/T, Y181C/I/V, Y188C/L/H, G190S/A, H221Y, P225H, F227C, M230I/L. NNRTI substitutions are tabulated by codon.
Integrase Gene Any Integrase Substitutions	At least one of the substitutions listed in the IAS-USA for integrase inhibitors T66I/A/K L74M E92Q/G, T97A

Table 9-2: Genotypic Substitutions

Category	Description of Relevant Substitutions
	F121Y
	E138A/K
	G140A/S
	Y143R/H/C, S147G, Q148H/K/R
	N155H
	Integrase substitutions are tabulated by codon

Phenotypic Resistance

The phenotypic resistance to a drug is defined as a fold change (i.e., ratio of the 50% inhibitory concentration (IC₅₀) of the clinical isolate to the IC₅₀ of the reference strain) greater than the cut-off for reduced susceptibility. The following table displays cut-offs used by Monogram Biosciences, Inc. to determine reduced susceptibility to each drug.

The phenotypic resistance status, as determined by Monogram (for ARVs other than BMS-955176) should be available in the clinical database. Hence, programming these cutoffs should be unnecessary.

Note: Monogram may use TFV as a code for tenofovir in phenotypic data files.

Table 9-3: Cut-offs used by Monogram Biosciences to Determine Reduced Susceptibility

Class	Drug	Reduced Susceptibility Cut-off
PI	Atazanovir (ATV)	2.2
	Atazanavir/Ritonavir (ATV/r)	5.2
	Darunavir/Ritonavir (DRV/r)	10
	Fosamprenavir/Ritonavir (AMP/r)	4
	Indinavir/Ritonavir (IDV/r)	10
	Lopinavir/Ritonavir (LPV/r)	9
	Nelfinavir (NFV)	3.6
	Ritonavir (RTV)	2.5
	Saquinavir/Ritonavir (SQV/r)	2.3
	Tipranavir/Ritonavir (TPV/r)	2
NNRTI	Delavirdine (DLV)	6.2
	Efavirenz (EFV)	3
	Etravirine (ETR)	2.9
	Nevirapine (NVP)	4.5

Table 9-3: Cut-offs used by Monogram Biosciences to Determine Reduced Susceptibility

Class	Drug	Reduced Susceptibility Cut-off
NRTI	Rilpivirine (RPV)	2.5
	Abacavir (ABC)	4.5
	Didanosine (ddI)	1.3
	Emtricitabine (FTC)	3.5
	Lamivudine (3TC)	3.5
	Stavudine (d4T)	1.7
	Tenofovir (TDF)	1.4
	Zidovudine (ZDV)	1.9
IN	Raltegravir (RAL)	2.2
	Dolutegravir (DTG)	4
	Elvitegravir (EVG)	3.5

